3.3.3 Exposure and Compliance variable

Exposure to the study therapy will be calculated as the difference between the last study therapy date and the first study therapy date converted to days plus 1 day. Any partial infusion will be considered as a complete infusion for the purpose of exposure, and the relevant details will be listed.

Compliance will be calculated as the sum of the actual infusions over all doses/expected infusions over all doses)*100.

4. ANALYSIS METHODS

4.1 General principles

All analyses will use SAS® version 9.1.3 or higher. Summary tables will be organized by age cohort and overall. All available data for each analysis set will be used in the analyses, and a subset of key safety, efficacy, and PK data will be included in listings. No statistical hypothesis testing will be performed. Confidence intervals (CI) will be two-sided 95% CIs.

Unless otherwise noted, categorical data will be presented using counts and percentages with the denominator for percentages being the number of patients in the analysis set by age cohort. Percentages will be rounded to one decimal place; except 0% and 100% will be displayed without any decimal places and percentages will not be displayed for zero counts. Continuous variables will be summarized using the number of observations (n), mean, SD, median, minimum, and maximum. The minimum and maximum values will be displayed to the same level of precision as the raw data, the mean and median to a further decimal place and the SD to two additional decimal places.

Imputation of missing data will be performed as described within this document (see [Section 3.2.1](#) for imputation of efficacy data at EOT and TOC and [Section 3.3.2](#) for imputation of partial dates for prior and concomitant medication). Visit windowing will be performed as described in [Section 3](#).

Baseline summaries will utilize the ITT and MITT Analysis Sets. Study therapy exposure, concomitant medication, and safety analyses will utilize the Safety Analysis Set. Efficacy analyses of clinical outcome and microbiological response will utilize the MITT and Micro-ITT Analysis Sets. PK analyses will utilize the PK Analysis Set. All data will be listed.

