8 June 2016	V2.0 Updated version of the SAP incorporating Protocol Amendment changes as outlined below: Change in definition of study day from “Study Day 1 is defined as the first day of study therapy administration.” to “Study Day 1 will start at the onset of study therapy and will end 24 hours later.”. Change in definition of cohort 2 from “Cohort 2: term neonates (defined as gestational age ≥38 weeks) aged 7 to ≤28 days ”. to “Cohort 2: term neonates (defined as gestational age ≥37 weeks) aged 7 to ≤28 days ”. Change in definition of cohort 3 from “Cohort 3: preterm neonates (defined as gestational age ≥34 to <38 weeks) aged 7 to ≤28 days ” to “Cohort 3: preterm neonates (defined as gestational age ≥34 to <37 weeks) aged 7 to ≤28 days ”. Change in dose from “Ceftaroline fosamil will be given at a dose of 4 mg/kg IV over 60 (± 10) minutes every 8 hours (q8h) (± 1 hour).” to “Ceftaroline fosamil will be given at a dose of 6 mg/kg IV over 60 (± 10) minutes every 8 hours (q8h) (± 1 hour).”. Change in requirements for administration of IV ampicillin and optional aminoglycoside from “IV ampicillin and optional aminoglycoside will be given as per standard of care.” to “IV ampicillin and optional aminoglycoside will be given as per standard of care. If the presence of an organism that requires treatment with ampicillin cannot be excluded, then the use of IV ampicillin for the first 48 hours is mandatory. If the result of additional microbiology, polymerase chain reaction or other investigations, indicate that ampicillin during the first 48 hours of treatment is not required, then its use is at the discretion of the investigator.”. In addition to the changes in relation to protocol amendments, additional tables were added for the duration of different Investigational Products (IP) [Ceftaroline, Ampicillin and Aminoglycoside]. Some additional programming notes were added to the shells to assist with the definition of variables within the derived/analysis datasets. An additional appendix was added to the SAP to list the criteria for potentially clinically significant laboratory tests. An additional appendix was added to the SAP to indicate the TFLs required for the Data Safety Monitoring Board (DSMB).

Date	Brief description of change
12 July 2016	V2.1 Updated to incorporate client review comments on V2.0. Updated to incorporate protocol amendment 2 changes: study medication dose changed from 4mg/kg to 6mg/kg.

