3. PRIMARY AND SECONDARY VARIABLES

For the calculation or derivations of the variables in this section, baseline will be defined as the last non-missing value before the start of study therapy. Change from baseline variables will be calculated for clinical laboratory tests and vital signs parameters as the post-treatment value minus the value at baseline. The visit windows for EOT, TOC, and SFU are defined in [Table 2](#) for efficacy analyses.

Study days are to be calculated starting from the onset of the first dose of study therapy, in 24-hour increments. If a date is prior to the first study therapy dose date (eg, date of LOS diagnosis, prior medication start date) then the study day will be calculated as (past date – first

study therapy dose date); if the assessment date is on or after the first study therapy dose date then the study day will be calculated as (assessment date – first study therapy dose date + 1). Durations in days will be calculated as (end date – start date +1).

Table 2 Visit Windows for EOT, TOC, and SFU

Visit	Protocol-defined Window
End of IV therapy (EOT)	Within 24 hours of completion of the last infusion of study drug
Test of cure (TOC)	8 to 15 days after the last dose of study drug
Safety follow-up (SFU)	28 to 35 days after the last dose of study drug

NB. Since there is no per protocol population defined for this study, scheduled visits will be used for MITT analyses and derived analysis windows will not be evaluated.

For analyses purposes, nominal visit data was used.

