4.2.6.2 Clinical laboratory safety assessment

Clinical laboratory data include hematology, chemistry, CRP, CSF, blood gas and base excess, urinalysis, and urine output. Descriptive statistics (including n, mean, SD, minimum, median, and maximum) of observed results and change from baseline will be presented for continuous clinical laboratory results by age cohort and overall for the Safety Analysis Set.

In addition, the following summaries at each applicable visit will also be provided by age cohort and overall:

- Shift tables showing the number of patients with changes from low, normal, or high values from baseline
- Shift tables showing the number of patients with urinalysis changes from baseline to each category (negative, trace, positive)
- The number and percentage of patients with abnormal values using the PCS criteria in [Appendix B](#)

Listings of values for each patient will be presented by age cohort with abnormal or out-of-range values flagged. All laboratory results for each patient will be listed for the Safety Analysis Set.

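### At visits where testing is optional, the by-visit percentages of infants with potentially clinically significant (PCS) laboratory values are lower bounds, and the SAP text describes no any-time PCS figure per infant

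*SAP*

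**What the plan says.** SAP 4.1 gives the general rule for categorical data. Where no section says otherwise, the tables give counts, and each percentage is formed "with the denominator for percentages being the number of patients in the analysis set by age cohort". It assigns safety analyses to the Safety Analysis Set, which SAP 2.1.2 defines by receipt of any ceftaroline fosamil, whether or not the infant was later tested. SAP 3.1.1 rules out imputation of missing safety data.

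SAP 4.2.6.2 then states that "the following summaries at each applicable visit will also be provided by age cohort and overall", and one of these summaries is "The number and percentage of patients with abnormal values using the PCS criteria" in Appendix B. It names no other denominator, does not ask for the number tested in that table, and describes no summary over the whole post-baseline period.

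The same section also plans descriptive statistics with n for continuous results. It adds "Shift tables showing the number of patients with changes from low, normal, or high values from baseline" and says that "All laboratory results for each patient will be listed for the Safety Analysis Set".

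Protocol 8.5.2 promises a summary of the incidence of selected PCS results and sets no time frame for it.

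**The concern.** A percentage over the whole Safety Analysis Set describes that set properly only if nearly everyone in it was tested. Here testing is sparse by design. An untested infant adds one to the denominator and can add nothing to the numerator. From the PCS table alone, a low percentage at test of cure (TOC) or safety follow-up (SFU) could mean few abnormal results or few tests.

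The second gap is the per-infant figure. One infant may be counted at several visits, so by-visit rows do not show how many infants ever had a PCS value. For a safety study of 24 infants, that is the natural reading of incidence.

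A smaller gap concerns unscheduled samples. Protocol 5.3.1 foresees them, and the SAP text does not say in which PCS row they are counted. On treatment, a clinically indicated draw falls within a study day, so the question arises mainly for results between EOT, TOC and SFU.

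**Working it through.** The plan states no PCS rate and no number tested per visit, so it has no figure to reproduce. Its only relevant number is the planned size, 3 cohorts × 8 = 24.

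**When blood count and chemistry are drawn (protocol)**

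| Time | Requirement | Section |
|---|---|---|
| Baseline | all infants | 4.1.1.2 |
| Days 1 to 14 | when clinically indicated; from Day 4, a recommendation to repeat at intervals of no more than 7 days | 4.2.1.3 to 4.2.4.3 |
| EOT | all infants | 4.2.5.2 |
| TOC | when clinically indicated; listed without that qualifier for infants already classed as clinical failures | 4.3.1.2, 4.3.1.3 |
| SFU | when clinically indicated, at an in-person visit; the visit may be by telephone | 4.3.2, 4.3.2.2 |

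Table 3 in protocol 5.8 agrees: it budgets these two samples only at baseline and EOT.

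**By-visit percentage.** Let N be the set size, m the number tested, x the number with a PCS value, and f the ratio of the PCS rate in untested infants to that in tested infants.

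- SAP default: x/N
- Percentage of those tested: x/m
- Logical range for the whole set: x/N to (x + N − m)/N
- Whole-set share for a given f: (x + (N − m) × f × x/m)/N

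The default is the lower end of the logical range. The values of x, m and f below are assumptions. With N = 24 and x = 2, the default is 2/24 = 8.3% in every row.

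| m | x/m | Logical upper end | f = 0.25 | f = 0.5 | Understatement by the default, in points |
|---|---|---|---|---|---|
| 22 (EOT-like) | 9.1% | 4/24 = 16.7% | 2.045/24 = 8.5% | 2.091/24 = 8.7% | 0.2 to 0.4 |
| 18 | 11.1% | 8/24 = 33.3% | 2.167/24 = 9.0% | 2.333/24 = 9.7% | 0.7 to 1.4 |
| 12 | 16.7% | 14/24 = 58.3% | 2.5/24 = 10.4% | 3.0/24 = 12.5% | 2.1 to 4.2 |

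The logical upper ends are implausible at optional visits, because most untested infants were untested for want of an indication. For the same reason x/m probably overstates the whole-set share. The same f is used in all rows so that they can be compared.

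**Any-time figure.** Suppose one analyte has PCS counts of 2, 2 and 1 at Day 3, EOT and TOC.

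- Fewest distinct infants: the largest count, 2, which is 2/24 = 8.3%
- Most distinct infants: the sum, 2 + 2 + 1 = 5, which is 5/24 = 20.8%

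In a cohort of 8 with counts 1, 1 and 1, the range is 1/8 = 12.5% to 3/8 = 37.5%. The by-visit rows are identical at both ends of each range.

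**The case against.** The strongest objection is that the point rests on SAP prose, while such details are often settled in table shells. The SAP amendment history shows that shells exist ("Some additional programming notes were added to the shells"), and they were not supplied. They may set another denominator, print the number tested or hold a worst-value row. This stands: the documents show that the SAP text is silent, and a reader should not infer that the final tables lack these items.

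Second, the information is not lost. The continuous tables give n, the shift tables run by visit, and every result is listed, so in about 24 infants the figures can be rebuilt. Protocol 6.2.2 also requires abnormal results to be recorded as adverse events if, for example, they come with symptoms or need intervention. The primary outcome measures in protocol 2.1 are adverse events, serious adverse events, deaths and discontinuations caused by adverse events, with laboratory data in support. All of this stands and limits the harm. The shift tables use low, normal and high categories and not the PCS limits, so a per-infant PCS count still has to come from the listings.

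Third, dividing by the whole set is a legitimate convention, and a percentage of those tested is no unbiased replacement. This also stands, and it is why the fix shows both numbers.

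Two stronger readings are tempting. A reader might infer from SAP 3 ("For analyses purposes, nominal visit data was used") that unscheduled results are dropped from the PCS rows. That note sits under visit windows introduced for efficacy analyses, and SAP 4.1 says that all available data will be used, which suggests they are kept. The text leaves open only where they are counted. A reader might also infer a departure from protocol 8.5.2. Because the protocol gives incidence no time frame, by-visit summaries do not breach it.

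**Conclusion.** The point holds as a reporting gap in the SAP text and is an optional improvement. Under the stated default, by-visit PCS percentages are lower bounds wherever testing is optional and close to exact at EOT. If untested infants have a quarter to a half of the tested rate, the default understates by 0.2 to 0.4 points with 22 of 24 tested and by up to about 4 points with 12 tested. Four points is one infant in 24.

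The missing any-time summary matters more: on the assumed counts, the same by-visit rows fit 2 to 5 infants. All these sizes depend on assumed counts, because the documents give no testing frequency or PCS rate. The conclusion also depends on the shells not already supplying the missing items.

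**What to change.** Change SAP 4.2.6.2 in two ways.

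1. For each analyte and visit, show the PCS count, the number tested and N, and label the denominator used. For the percent-change criteria in Appendix B, the number tested should be those who also have a baseline value. If a percentage of those tested is shown, note that testing for cause probably makes it too high for the whole cohort.
2. Add a row for the worst post-baseline value at any time, for each analyte and each direction that Appendix B defines. Include unscheduled samples, use infants with at least one post-baseline value as the denominator, and make this row the headline PCS incidence.

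If the shells already do this, one sentence in the SAP saying so is enough.

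The cost is SAP wording, an extra column and one derived worst-value record per analyte and direction. No new data or blood are needed. The downside is a headline percentage that may be clearly higher than any single by-visit figure, because the numerator changes as well as the denominator. On the assumed counts, with 22 infants having a post-baseline value, it would lie between 2/22 = 9.1% and 5/22 = 22.7%, against a largest by-visit figure of 8.3%.

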4.1.1 Data quality

The clinical database will be cleaned prior to analysis; see PRA Clinical Informatics Plan for details. Beyond the data screening built into the PRA Clinical Informatics Plan, the PRA programming of analysis datasets, tables, figures, and listings (TFLs) will provide additional data screening.

Review of a pre-freeze TFL run on clean patients and a post-freeze TFL run on the frozen database will allow for further data screening prior to lock. The post-freeze TFL will be discussed with Pfizer in a data review meeting to identify any final data issues and seek corrections prior to database lock. The PRA statistician and Pfizer must approve database lock.

PRA's goal is to ensure that each TFL delivery is submitted to the highest level of quality. Our quality control procedures will be documented separately in the study-specific clinical programming quality control plan.

4.2 Analysis methods

4.2.1 Patient disposition

The number and percentage of patients enrolled and treated with study therapy, along with the number and percentage of treatment completers, premature discontinuations from study

therapy administration, and withdrawals from the study will be provided overall and within each age cohort based for all patients, ie, all subjects who signed informed consent.

Disposition details for subjects who discontinued from the study and from study therapy; and those who completed the study will be listed for all patients.

The number of patients in each analysis set and the reasons for exclusion from analysis sets will be listed and summarized for the ITT Analysis Set.

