3.10.1. Screen failures

Screen failures are patients who do not fulfil the eligibility criteria for the study, and therefore must not be included in the study. These patients should have the reason for study withdrawal recorded as 'Incorrect Enrolment' (ie, patient does not meet the required inclusion/exclusion criteria). This reason for study withdrawal is only valid for screen failures.

Where a patient is incorrectly started on treatment the patient may continue or discontinue treatment, depending on the outcome of the discussion between the Sponsor study physician/designee and the investigator.

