4.1. Baseline

Informed consent in writing will be obtained from parent(s) or legally-acceptable representative(s) before initiating any study assessment or procedure.

Baseline procedures must be completed within 36 hours before the start of the first dose of study therapy. If any such procedures have been carried out as standard-of-care within the timeframe they can be considered as baseline procedures. Potential patients who do not meet entrance criteria may, as appropriate, repeat Baseline evaluations at a later time for possible enrolment into the study.

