4.1.1.3. Microbiological assessments

Microbiological assessments should be performed preferably before any antibiotics are administered.

- If clinically indicated and performed as part of patient's regular medical care, obtain blood and urine samples for testing per [Section 5.2.1](#) and [5.2.2](#), respectively; cultures should be repeated per standard of care upon knowledge of a positive result until sterilization is confirmed
- If clinically indicated and performed as part of patient's regular medical care, obtain CSF or other specimens/tissue samples per [Section 5.2.3](#) and [5.2.4](#), respectively; cultures may be repeated per standard of care upon knowledge of a positive result.
- Obtain any prior microbiological and clinical data (eg, notes in medical records confirming worsening of signs and symptoms of sepsis) that may help determine eligibility ([Section 5.2](#))

Enrol the patient and assign to PK schedule after verifying that the patient meets all inclusion and no exclusion criteria. There should be no medically inappropriate delay in administration of study therapy.

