8.3.1. Intent-to-treat analysis set

The Intent-to-Treat (ITT) Analysis Set will consist of all enrolled patients.

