8.5.1. Analysis of the study population and patient characteristics

Patient disposition (enrolment, discontinuations from the study) overall and within each age cohort will be provided based on the ITT Analysis Set. Reasons for exclusion from study analysis sets will be summarized for the ITT Analysis Set.

Demographics (age, race, gender), medical and surgical history including antepartum/peripartum period, baseline assessment of the clinical signs and symptoms of LOS, microbiological assessment of blood, CSF, urine, and other specimens or tissue samples will also be summarized for the ITT Analysis Set.

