2.1.1 Intent-to-treat Analysis Set

The Intent-to-treat (ITT) Analysis Set will consist of all enrolled patients for whom informed consent form (ICF) was signed.

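### SAP 4.2.1 takes disposition percentages over everyone who signed consent rather than ITT, so any screen failures dilute the therapy completion and discontinuation percentages and distort study withdrawal in a direction the SAP leaves open

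*SAP*

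**What the plan says.** Protocol 8.5.1: "Patient disposition (enrolment, discontinuations from the study) overall and within each age cohort will be provided based on the ITT Analysis Set". Protocol 8.3.1 defines that set: "The Intent-to-Treat (ITT) Analysis Set will consist of all enrolled patients". SAP 2.1.1 defines it as "all enrolled patients for whom informed consent form (ICF) was signed".

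The first paragraph of SAP 4.2.1 covers five items: patients enrolled, treated, completing treatment, stopping study therapy early and withdrawing from the study. All five are to be given as number and percentage, and the sentence ends: "withdrawals from the study will be provided overall and within each age cohort based for all patients, ie, all subjects who signed informed consent". Its third paragraph uses ITT, but only for analysis-set membership and reasons for exclusion.

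Three protocol rules show who is in the consented group:

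- Section 4.1: "Informed consent in writing will be obtained from parent(s) or legally-acceptable representative(s) before initiating any study assessment or procedure".
- Section 4.1.1.3: "Enrol the patient and assign to PK schedule after verifying that the patient meets all inclusion and no exclusion criteria".
- Section 3.10.1, on screen failures: "These patients should have the reason for study withdrawal recorded as" 'Incorrect Enrolment'. The same section reserves that reason for screen failures.

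**The concern.** A screen failure has signed consent but should not be enrolled or dosed, and so can neither complete nor stop study therapy. Placing such infants in the denominator makes the completion and discontinuation percentages describe a group that was largely, but not wholly, treated. For study withdrawal the screen failure may also enter the numerator, because sites are told to record a reason for withdrawal.

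The study is descriptive, with 24 patients in three cohorts of 8. Readers will use the disposition table to judge how many treated infants finished therapy and how complete follow-up was. A few screen failures can shift those percentages visibly, most of all within a cohort.

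**Working it through.** **The plan's own figure.** 3 cohorts x 8 = 24 patients (protocol 8.2, SAP 1.3). Neither document gives a screen-failure count or an expected disposition rate, so there is nothing further to reproduce.

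**Are the two populations different?** Consent precedes every study procedure, enrolment follows verified eligibility, and ITT requires enrolment under both definitions. A consented infant who fails screening is therefore in the SAP 4.2.1 base and not in ITT. SAP 4.2.1 itself reports the percentage enrolled among those consented. That row would always be 100% if the two groups were the same.

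**Notation.** T = treated, E = enrolled (ITT), s = screen failures, x = early stops of study therapy, w = study withdrawals among enrolled patients. Consented N = E + s. For illustration E = T = 24. E could be somewhat larger, because protocol 3.3 replaces patients withdrawn before any dose. The values of s, x and w are assumed.

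**Therapy discontinuation and completion.** On the SAP base, discontinuation is x/(24 + s), against x/24 among treated patients. The relative fall is 1 - 24/N and does not depend on x. Completion, taken here as (24 - x), is diluted by the same factor. With x = 3:

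| s | N | Relative fall | Discontinued, SAP base | Discontinued, treated | Completed, SAP base | Completed, treated |
|---|---|---|---|---|---|---|
| 0 | 24 | 0% | 3/24 = 12.5% | 12.5% | 21/24 = 87.5% | 87.5% |
| 3 | 27 | 11.1% | 3/27 = 11.1% | 12.5% | 21/27 = 77.8% | 87.5% |
| 6 | 30 | 20.0% | 3/30 = 10.0% | 12.5% | 21/30 = 70.0% | 87.5% |
| 12 | 36 | 33.3% | 3/36 = 8.3% | 12.5% | 21/36 = 58.3% | 87.5% |

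**Study withdrawal.** On ITT the rate is w/E. On the SAP base it is (w + s)/(E + s) if screen failures are counted as withdrawals, and w/(E + s) if they are not. With w = 2 and E = 24:

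| s | ITT | SAP base, screen failures counted | SAP base, not counted |
|---|---|---|---|
| 0 | 2/24 = 8.3% | 8.3% | 8.3% |
| 3 | 8.3% | 5/27 = 18.5% | 2/27 = 7.4% |
| 6 | 8.3% | 8/30 = 26.7% | 2/30 = 6.7% |
| 12 | 8.3% | 14/36 = 38.9% | 2/36 = 5.6% |

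The directions are general. (w + s)/(E + s) - w/E = s(E - w)/[E(E + s)], which is positive whenever s >= 1 and w < E. And w/(E + s) is below w/E whenever s >= 1 and w >= 1.

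**One cohort of 8, one event, two screen failures.** Therapy discontinuation is 1/10 = 10.0% instead of 1/8 = 12.5%. Withdrawal is 3/10 = 30.0% if screen failures are counted and 1/10 = 10.0% if not, instead of 12.5%. A screen failure outside the age or gestational-age limits belongs to no cohort, so the cohort columns may not add to the overall column.

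**The case against.** **The base may be only a table population.** SAP 4.2.1 names the population for the table and does not give a denominator row by row. SAP 4.1 defaults to the number in the analysis set, and the consented group is not among the sets defined in SAP section 2. The table shells, which might settle the matter, are not in these documents. That leaves some doubt about how the table would be programmed. But the only population the paragraph names for its percentages is the consented one, and nothing in it narrows the base for the therapy rows.

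**'Enrolled' is used loosely.** Protocol 3.4 speaks of patients enrolled and then found ineligible, and the screen-failure code itself contains the word. The SAP phrase could be a careless restatement of ITT. The order set in protocol 4.1.1.3, the SAP's own enrolled row and its separate mention of ITT in the same section all count against this.

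**Withdrawal need not be inflated.** A reader might infer from protocol 3.10.1 that the withdrawal percentage must come out too high. The documents do not support that. SAP 4.2.1 does not say whether those records count as withdrawals, and because the code is reserved for screen failures they can be separated. If they are left out, the rate is too low instead. This part of the objection stands.

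**The protocol conflict is narrower than the whole table.** Protocol 8.5.1 names only enrolment and discontinuation from the study. It sets no base for completing or stopping therapy, so the treated denominator proposed for those rows rests on statistical sense and not on a protocol instruction. This also stands.

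**The effect may be small.** Standard-of-care results from the preceding 36 hours can serve as baseline, so eligibility may often be largely known before consent and screen failures may be few. Counts accompany the percentages and the number treated is in the same table, so a reader could recompute the rates.

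**Conclusion.** The point holds as a minor one. For study withdrawal, the SAP's base departs from the protocol's stated ITT base. For treatment completion and therapy discontinuation, the SAP's base includes infants who could have had neither outcome. If there is at least one screen failure, the completion and discontinuation percentages fall by a relative 1 - 24/N wherever they are above zero: 11%, 20% and 33% for an assumed 27, 30 and 36 consented. The withdrawal percentage is distorted too, upward or downward according to a choice the SAP leaves open. With no screen failures, and every enrolled patient treated, the bases agree.

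A reader might also infer that the primary tolerability result is affected. It is not. AEs leading to discontinuation are summarised on the Safety Analysis Set (SAP 4.2.6.1), as are exposure and compliance (SAP 4.2.5), and no hypothesis is tested. The harm is confined to one descriptive table.

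The size rests on assumed screen-failure counts, on 24 treated and on all enrolled patients being treated. The direction for therapy completion and discontinuation rests only on applying SAP 4.2.1 as written.

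**What to change.** Amend SAP 4.2.1 and the disposition table as follows:

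- Show the numbers consented and failing screening as counts only, with no percentage.
- Use ITT as the denominator for study withdrawal, as protocol 8.5.1 states, and exclude 'Incorrect Enrolment' screen failures from that row.
- Use treated patients (the Safety Analysis Set) as the denominator for treatment completion and premature discontinuation of study therapy.
- State the denominator for each block of rows in a footnote.

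The cost is a few lines of SAP text and the denominators of one table. No new data are needed: consent, enrolment, dosing and the reason code are already collected.
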